9.2 SAFETY OVERSIGHT

Safety oversight will be under the direction of the PI, who will review AEs in real time and make decisions regarding a participant's continuation of the clinical trial.

9.3 EARLY WITHDRAWAL OF PARTICIPANTS

9.3.1 REASONS FOR WITHDRAWAL

A study participant will be discontinued from further participation if:

- The participant meets any exclusion criteria (either newly developed or not previously recognized).
- Anything that, in the opinion of the investigator, would place the participant at increased risk or preclude the participant's full compliance with or completion of the study.

Participants are free to withdraw from participation in the study at any time upon request.

9.3.2 DATA COLLECTION FOR WITHDRAWN PARTICIPANTS

We will collect safety data on any participant discontinued because of an AE or SAE. In any case, every effort will be made to undertake protocol-specific follow-up procedures. If voluntary withdrawal occurs, the participant will be asked to continue scheduled evaluations and complete an end-of-study evaluation.

If an AE has been reported, researchers will help the participant seek the medical care they need and a follow-up will be performed by the PI. In the case of an early withdrawal, the researcher will make a note to file indicating this.

9.4 TERMINATION OF STUDY

If a seizure occurs at the time of a study visit, a temporary hold will be placed over the study and further investigation will ensue. This could lead to stopping the study prematurely or continuing on with further safety measures in place. If two seizures are witnessed during the study visits, the entire study will be stopped prematurely. These individuals would be referred for further medical attention. It is very unlikely that a seizure will occur.

The study will also be stopped (at least temporarily) if studies provide evidence that transcranial current/magnetic stimulation caused brain damage or other harmful effects on participants, either short-term or long-term.

Examples of findings that might trigger a safety review are the number of SAEs overall, the number of occurrences of a particular type of SAE, severe AEs/reactions, or increased frequency of events.

The IRB will also be informed promptly and provided the reason(s) for the termination of suspension of by the investigator, as specified by the applicable regulatory requirement(s).

10 SAFETY & REPORTING

It is important to assess safety over the course of this study. This section describes in detail how safety is assessed, reporting of Adverse Events, Serious Adverse Events, and Unanticipated Problems. This section is a reference for internal use.

10.1 SAFETY PARAMETERS

STIMULATION SIDE EFFECTS. A stimulation adverse effects questionnaire used in previous studies will be administered at the end of each stimulation. This questionnaire will be used as a safety measure and to collect data on participant experience. The adverse effects questionnaire asks participants to respond on a 4 point Likert scale on the severity of symptoms experienced during the stimulation session (1 = absent, 2 = mild, 3 = moderate, 4 = severe). The side effects listed are headache, neck pain, scalp pain, tingling, itching, ringing/buzzing noise, burning sensation, local redness, sleepiness, trouble concentrating, improved mood, worsening of mood, dizziness, flickering lights, and other (specify). Participants are also asked to rate on a 5 point Likert scale how related they believe the side effects to be to stimulation (1 = no relation, 2 = remote, 3 = possible, 4 = probable, 5 = definite).

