5.2 STIMULATION SESSIONS

Participants will undergo four sessions: one screening, one baseline, and two active sessions. During all four sessions, participants will be guided through the consent form. To ensure that all aspects of the research are understood, participants may be asked a series of questions about the research they are about to take part in (*Appendix E*). Once it is clear that the participant understands the consent form they may sign the form.

Session 1: Screening

- In this initial session, participants will be explained the procedure and reminded of their expectations and rights (informed consent). After obtaining consent, a pregnancy screening will be administered. Following this the participant will practice and perform cognitive control task. Participants have a self-paced break between blocks of the task.
- Participant will receive \$20 in compensation

Session 2: Baseline

- The following questionnaires will be administered during the session or will be completed remotely by the participant through an online survey weblink before the session - These measures are listed below under "self-report measures"
- Preparation - The EEG net will be applied. Resting state EEG – Participant will be asked to relax with eyes open and eyes-closed while EEG is collected simultaneously. Following this the participant will practice and perform cognitive control task. Motor thresholding using single pulse TMS for use in future sessions (performed once for each participant, either on Baseline or Stimulation 1 day). Electrodes and net will be removed and participant can wash their hair and face. Participant will receive \$30 in compensation

CONFIDENTIAL

Session 3 and 4: Stimulation 1 and 2

- The procedure for these sessions will follow the same timeline as the second, with the exclusion of informed consent, questionnaires. Motor threshold may be performed on Stimulation 1 day if it was not done during the Baseline session.
- Before practice and performance of the cognitive control task, the TMS coil will be positioned over the targeted region. During performance of the task, stimulation will be delivered on every trial. At the end of the session, participants will receive \$40, and \$60 in compensation for sessions 3, and 4, respectively.

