6.2 SPECIAL ASSAYS OR PROCEDURES

Each participant will receive stimulation on all four sessions, separated by a week. The baseline session will involve single pulse TMS for calculating the motor threshold. The other three sessions will involve train of rhythmic TMS during performance of a cognitive control task. For stimulation day, the rhythmic TMS trains are delivered on every trial of the task (there are 600 trials per session). Each train of TMS consists of 5 pulses. There will be a total of 2400 pulses delivered per session. Each TMS train will be separated by a minimum of 5 seconds. There are three possible trains: alpha frequency with a 100 milliseconds inter-pulse interval, theta frequency with a 200 milliseconds inter-pulse interval, and arrhythmic with a variable inter-pulse interval (not to exceed a minimum of 20 milliseconds inter-pulse interval). The inter-pulse interval, inter-train interval, number of trains, and TMS intensity are all under the safety guidelines set forth by Rossi et al. 2009 and is typical for experiments that deliver online TMS (Hanslmayr et al. 2014; Albouy et al. 2017).

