6.3 SAFETY MEASURES

We will be monitoring the safety of our participants throughout the study with the following measures. These measures are listed below and can be found in the attached documents.

- A. A stimulation adverse effects questionnaire used in previous studies (IRB #14-1622, #14-3285, and #14-0600) will be administered at the end of each stimulation session. This questionnaire will be used as a safety measure and to collect data on participant experience. Please see *9.1 Safety Parameters* for more information.

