11.3 DATA MANAGEMENT

Data will be stored in a password-protected cloud-based data system that does not contain any participant information. Individual records are referred to by dummy identifiers that cannot be traced back to the study participants except with the master code list that is stored separately in a secured location.

Information about study participants will be kept confidential and managed according to the requirements of the Health Insurance Portability and Accountability Act of 1996 (HIPAA). Those regulations require a signed participant authorization informing the participant of the following:

- What protected health information (PHI) will be collected from the participants in this study
- Who will have access to that information and why
- Who will use or disclose that information
- The rights of a research participant to revoke their authorization for use of their PHI.

In the event that a participant revokes authorization to collect or use PHI, the investigator, by regulation, retains the ability to use all information collected prior to the revocation of participant authorization. For participants that

have revoked authorization to collect or use PHI, attempts should be made to obtain permission to collect at least vital status (i.e., that the participant is alive) at the end of their scheduled study period.

The responsibilities designated to each member of the research team are documented on the Delegation of Authority Form. The study coordinator and research assistants will be responsible for the informed consent process, review for eligibility, questionnaire administration, data entry, device administration, EEG administration, and CRF entries. The study coordinator will be responsible for AE/SAE documentation and reporting, while the PI will be responsible for the AE assessment, review of the AE documentation forms, and overview of the research staff.

All data (including AEs, concomitant medications, and expected adverse reactions data) will be entered into a data capture system provided by REDCap. The data system includes password protection and internal quality checks, such as automatic range checks, to identify data that appear inconsistent, incomplete, or inaccurate. Clinical data will be entered directly from the source documents.

All assessments completed by the participant at home will be completed via REDCap as well, ensuring participant security and confidentiality.

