APPENDIX A: SCHEDULE OF EVENTS

	Telephone Screening Interview	Session 1: Screening	Session 2: Baseline	Sessions 3 & 4: Stimulation
Procedures				
Provide Verbal Consent	x			
Signed Consent Form		x		
Assessment of Eligibility Criteria	x	x		
Urine Pregnancy Test		x		
Baseline Self-Report Assessments			x	
Baseline EEG (Resting state)			x	x
Cognitive control task		x	x	x
Task EEG (during cognitive control task)			x	x
Stimulation during task				x
Stimulation Questionnaire				x

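### No question about symptoms that begin after a participant leaves a stimulation session is scheduled, so later events enter the safety record only if volunteered

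*Combined protocol and SAP*

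**What the plan says.** The structured safety instrument is a side-effects questionnaire that, under Section 6.3, "will be administered at the end of each stimulation session". Section 10.1 describes it as a four-point rating "on the severity of symptoms experienced during the stimulation session". Sections 8.2.1 and 8.3 add staff checks, also while stimulation is under way.

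The last column of Appendix A is "Sessions 3 & 4: Stimulation"; no later visit, call or survey is listed. For Sessions 3 and 4, Section 5.2 states: "The procedure for these sessions will follow the same timeline as the second, with the exclusion of informed consent, questionnaires". The one question the plan asks about the time between sessions concerns pregnancy, and it is put to female participants only (Sections 9.3.1, Pregnancy follow-up, and 11.3.1).

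Other provisions bear on later events:
- Section 3.3.2 plans a reminder call or email before upcoming sessions and makes staff reachable by phone and email.
- Section 10.2.1 says that all AEs go on a CRF and are followed to resolution. It also says that a medical condition noted at the stimulation session counts as baseline and is not an AE.
- Section 10.4 sets follow-up within one week of an AE.
- Section 9.3.2 says that, on voluntary withdrawal, "the participant will be asked to continue scheduled evaluations and complete an end-of-study evaluation".
- Section 9.4 gives examples of findings that might trigger a safety review, among them "severe AEs/reactions, or increased frequency of events".

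**The concern.** Both the timing of the questionnaire and its recall window stop at the end of the session. Several listed items (headache, neck pain, ringing or buzzing, worsened mood) could in principle begin after the participant has gone home, and no one is scheduled to ask about that period.

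At stake is what the event counts in Section 9.4 mean. They would combine symptoms elicited item by item during a session with later events that reach the team only when a participant reports them. A low count of later events could mean that few occurred or that few were volunteered, and the record could not tell these apart. The baseline sentence in Section 10.2.1 adds a second route by which a reported event could be lost.

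**Working it through.** The plan states no figure on this point, so there is none to reproduce. The check is a reading of each provision that could capture an event starting after departure, followed by a count of exposures.

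**Step 1. Which provisions ask about the period after departure?**

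1. Questionnaire (Sections 6.3, 10.1): completed at session end and about that session. Does not ask.
2. Staff checks (Sections 8.2.1, 8.3): made during stimulation. Do not ask.
3. Reminder contact (Section 3.3.2): falls between Sessions 3 and 4 and is an opportunity to report. No symptom question is specified.
4. Session 4 (Section 5.2, Appendix A): takes place after Session 3 but lists no symptom question for the interval. The questionnaires that Section 5.2 drops are the baseline self-report ones; the end-of-session side-effects form is still given, but it covers Session 4 itself.
5. Pregnancy question: covers the interval, but not symptoms, and not all participants.
6. AE capture (Section 10.2.1): gives no method or time window for asking, although the heading of Section 10.2 promises methods and timing.
7. AE follow-up (Section 10.4): starts once an AE is known.
8. End-of-study evaluation (Section 9.3.2): named only for voluntary withdrawal, with no defined content or timing, and absent from Appendix A.

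None is a scheduled question about symptoms that start after leaving.

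**Step 2. What happens to an event that is volunteered?**

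Take an event that begins after Session 3 and is first mentioned at Session 4. Under the all-AEs statement in Section 10.2.1 it is an AE. Under the baseline sentence in the same section it is a condition noted at the stimulation session, hence not reported. The two sentences give opposite results for the same event.

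**Step 3. How many exposures are affected?**

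Inputs: 48 completers (Section 3); two sessions with rhythmic TMS each (Sections 4 and 5.2).

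- Exposures: 48 × 2 = 96.
- With a scheduled symptom question about the time after leaving: 0 of 96.
- Followed by another scheduled visit: the 48 first stimulation sessions.
- With no later scheduled contact: 96 − 48 = 48.

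Section 6.2 conflicts on the session count. It says "Each participant will receive stimulation on all four sessions, separated by a week" and assigns rhythmic trains to three of the four. On that count there are 48 × 3 = 144 exposures. Still none has a scheduled question, and still 48 are last sessions. The passages must be reconciled, but the finding does not turn on which count is right. Participants who have a stimulation session but do not complete (up to 100 may be enrolled) would add to either total.

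**The case against.** The plan is not silent on later events. All AEs and SAEs are to be recorded however they become known, staff can be reached by phone or email, a reminder contact falls before Session 4, and known AEs are followed up. The review triggers in Section 9.4 also include SAEs and severe AEs, which participants are more likely to report unprompted. The likely loss is mild, self-limited events. This stands and limits the point to the absence of scheduled elicitation.

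A reader might infer more in three ways.

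- **That there is no contact at all between or after sessions.** The documents do not support this: Section 3.3.2 plans the reminder, Sections 10.2.1 and 10.4 require follow-up of known AEs, and Section 13.6 has participants, including completers, notified if the study is discontinued.
- **That a reported safety rate would be invalid.** One can compute that zero events in 48 participants gives a one-sided 95% upper bound of 1 − 0.05^(1/48) = 6.05%, and argue that it holds only for in-session events. But the plan promises no safety rate, final AE table or safety endpoint; its outcomes are working memory capacity, spectral power and response time. The bound would qualify a claim that nobody makes.
- **That delayed events are common here.** The documents give no rate. Section 4 says that rhythmic effects fade within a few cycles, but that concerns oscillations, not side effects, and settles nothing either way.

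The questionnaire itself and the consent pages are not visible. They may tell participants to report later symptoms, so the point rests on the description in Section 10.1 and on Appendix A.

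**Conclusion.** The point holds as a modest gap in safety data collection. The visible documents schedule no question about symptoms starting after a stimulation session: 0 of 96 exposures among completers (0 of 144 on the Section 6.2 count), and for the last 48 there is no later scheduled contact. The counts that may prompt a safety review therefore mix actively elicited in-session symptoms with passively reported later ones. The baseline sentence in Section 10.2.1 conflicts with the all-AEs statement beside it and, read literally, could exclude an event first raised at Session 4. A narrower reading, that it means conditions present before any stimulation, is possible but is not what the sentence says.

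This assumes that the unseen questionnaire matches its description in Section 10.1 and that Appendix A is the full schedule. How many events would be missed cannot be estimated from the documents. The primary and secondary analyses are unaffected.

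**What to change.** 1. At the start of Session 4, next to the existing pregnancy question but for every participant, ask about symptoms since the previous session. If reconciling Section 6.2 leaves more stimulation sessions, ask at each one after the first.
2. Add one row to Appendix A: a single REDCap survey after the last stimulation session attended, using the existing questionnaire reworded to cover the time since leaving, with timing for the sponsor to set. Send it also to participants who withdraw after a stimulation session, and reconcile it with the end-of-study evaluation in Section 9.3.2. That evaluation cannot simply be a post-Session-4 survey, because a participant may withdraw earlier. The infrastructure exists, since Section 11.3 says "All assessments completed by the participant at home will be completed via REDCap as well".
3. Reconcile the baseline sentence in Section 10.2.1 with the all-AEs statement, so that conditions arising after the first stimulation session are not classed as baseline.
4. Report events collected this way separately from in-session symptoms.

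The cost is a protocol amendment and one short survey per participant: 48 for completers, plus those withdrawing after a stimulation session, and at most 100 in all if everyone enrolled received one. There is also a real processing load. The questionnaire includes ordinary experiences such as sleepiness, trouble concentrating and improved mood. Each one recorded as an AE needs a report form, PI review and follow-up under Sections 10.2.1 and 10.4.

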10.2 METHODS AND TIMING FOR ASSESSING, RECORDING, AND ANALYZING SAFETY PARAMETERS

10.2.1 ADVERSE EVENTS

All AEs, including local and systemic reactions not meeting the criteria for “serious adverse events”, will be captured on the appropriate CRF. In addition, the AE Report Form will be completed by the study coordinator (Appendix B). The AE Report Form includes the following:

- What is known about the therapy
- What is known about previous reported side effects
- If the AE occurred in temporal relation to the therapy
- Whether or not the AE improves or disappears when treatment is stopped
- Whether the AE is worsening of baseline symptoms
- Whether the AE is related to concurrent medical condition or medication use

Once complete, this form will be given to the PI, who will review, comment, and sign this form. Completed forms will be placed in the participant’s folder.

In addition, the study coordinator will document any AE occurrence on the AE log (*Appendix D*), which includes information such as the date of the AE, severity, relationship to the treatment (assessed by the PI*), actions taken, and outcome(s). The log will be reviewed and initialed by the PI 72 hours after being completed. All AEs will be followed to adequate resolution and will be graded for severity and relationship to study. Any medical condition noted at the stimulation session will be considered at baseline and not reported as an AE.

***Relationship to Study Products:** The PI will determine whether an AE is associated with the study treatment. The event will be labeled associated if the event is temporally related to the administration of a therapy and no other factors can explain the event. The event will be labeled as not associated if the event is temporally independent of the study treatment and can be explained by external factors, such as major life events.

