5.1 SCREENING

The phone screening allows researchers to screen out participants based on self-report responses and for potential participants to become familiar with the study schedule, including procedures. During the telephone screening, researchers will provide a brief background about TMS. The timeline of visits will be explained, including the number of visits and the time commitment required. The participant will be informed of compensation, both amount and payment schedule. The participant will be asked if they have any questions. Once all questions have been answered, the participant will be asked if he/she is still interested in participating in the study. If yes, the researcher will ask if the participant will provide verbal consent to begin the initial phone screening which will determine eligibility for the stimulation session. *A telephone script, which includes the screening questions, is provided in Appendix G.* If the participant meets initial criteria with these two assessments, the stimulation session will be scheduled and a reminder call or email will be given at least 24 hours before the stimulation session.

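### The AE baseline rule in Section 10.2.1 does not fit two stimulation sessions: as written, a non-serious condition that starts after TMS and is noted at a later stimulation session is not recorded as an AE

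*Combined protocol and SAP*

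**What the plan says.** The rule is the last sentence of the AE recording procedure in Section 10.2.1 (Adverse Events): "Any medical condition noted at the stimulation session will be considered at baseline and not reported as an AE". It does not say which session is meant, whether it applies before or after the pulses are given, or when baseline ends.

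Section 5.2 sets out "one screening, one baseline, and two active sessions", and names the last two under "Session 3 and 4: Stimulation 1 and 2". On thresholding it adds: "Motor threshold may be performed on Stimulation 1 day if it was not done during the Baseline session". TMS may therefore first be given at the Baseline visit.

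Section 10.2.1 also says what follows once an event counts as an AE: a report form reviewed by the PI, and a log entry that includes the PI's judgement of relatedness. Section 10.4 adds follow-up within one week.

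**The concern.** A baseline rule for AEs should separate what a participant brought into the study from what arose in it. This one ties baseline to a visit type that happens twice, the second time a full stimulation session after the first. A participant who develops, say, a persistent non-serious complaint after Stimulation 1 and mentions it at Stimulation 2 has had it noted at a stimulation session. The sentence then says that it is baseline and is not reported.

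At stake is the formal record of non-serious events that begin between sessions: the AE form, the log entry, the relatedness assessment and the scheduled follow-up. Staff members who read the sentence differently could also classify the same complaint differently.

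**Working it through.** No stated figure needs reproducing and no calculation applies. The check sets the passages side by side and asks whether any of them supplies the missing cut-off.

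**Step 1. Does the phrase identify one visit?** The sections describe TMS exposure differently:

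| Place | Sessions described as involving TMS |
|---|---|
| Section 2.2 | Motor thresholding at the first session; stimulation on later days |
| Section 4 | Thresholding at Baseline or Stimulation 1; rhythmic TMS at the third and fourth sessions |
| Section 5.1 | One session, booked after the phone screen: "the stimulation session will be scheduled" |
| Section 5.2 | Two active sessions; thresholding at Baseline or Stimulation 1 |
| Section 6.2 | "Each participant will receive stimulation on all four sessions, separated by a week"; then, after the baseline session, "The other three sessions will involve train of rhythmic TMS" |
| Appendix A | Stimulation during the task at Sessions 3 and 4 |

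Only Section 5.1 describes a single stimulation session. Under every other description there is more than one, so the phrase does not fix a point in time.

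**Step 2. Apply the rule as written.** Take the schedule in Section 5.2. TMS is given at Stimulation 1, a non-serious condition begins afterwards, and it is noted at Stimulation 2. It meets the condition in the sentence, so it is classed as baseline. The same happens if thresholding was done at Baseline and the condition is noted at Stimulation 1. Under Section 2.2, exposure could start one visit earlier again.

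**Step 3. Does another rule bring the condition back?**

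- Section 10.2.1 requires all AEs to be captured and logged, but only what counts as an AE. The baseline sentence removes the condition from that class.
- The side-effects questionnaire is given after stimulation and, as Section 10.1 describes it, asks about symptoms during that session. A condition that began between visits falls outside that window. Section 8.3 is worded more loosely, so the questionnaire is a partial backstop. Appendix A lists it only for Sessions 3 and 4, so none is scheduled after thresholding at Baseline.
- The AE form (Section 10.2.1 and Appendix B) asks whether the event worsens a baseline symptom. That assumes a baseline but does not date it.
- SAEs and unexpected events have their own recording rules in Section 10, which do not depend on this sentence. The seizure provisions in Sections 8.3 and 9.4 do not either.

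Nothing in the available text sets a different cut-off for non-serious conditions.

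**Step 4. What is lost?** Without AE status there is no AE form, log entry or PI relatedness determination (Section 10.2.1), and the one-week follow-up in Section 10.4 is not triggered.

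**The case against.** The strongest reply is that no sensible reader would apply the sentence this way. It reads like wording left from a single-session study. In Section 5.1 the stimulation session is the visit booked straight after phone screening, which would be a reasonable AE baseline. The likely purpose was to keep pre-existing conditions out of the AE log, and if staff follow that purpose nothing is lost. This stands as an account of intent. It does not rescue the rule, because Sections 4 and 5.2 and Appendix A all provide for two stimulation sessions and the sentence was not adapted to them.

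A second reply is that the PI may learn of such a condition anyway. Section 9.1 makes the coordinator responsible for reporting all events to the PI, and refers to a reporting decision tree that is not in the text. Section 9.3.1 requires withdrawal for newly developed exclusion criteria or increased risk, whatever the AE label. This also stands. A reader might infer that affected events would escape the PI altogether; the documents do not support that. What would be missed is the formal record and the steps attached to it.

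Third, staff do have information from before stimulation. Section 6.1 asks about medical history and medication, and Appendix A places eligibility checks at the phone screen and Session 1. So they could often tell that a complaint is new. The rule as worded does not ask them to.

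A reader might also infer that the sentence removes every reaction during Sessions 3 and 4 from AE reporting. Read literally it could, but the AE form's questions on timing relative to stimulation and on improvement when it stops, together with the end-of-session questionnaire, show that this is not the plan.

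**Conclusion.** The point holds as a minor defect in safety recording. Followed as written under the two-session schedule, the sentence excludes from AE recording a non-serious condition that starts after a TMS exposure and is noted at a later stimulation session, and no other provision reverses that. This rests on the sentence being applied literally; under the probable intent the effect is nil.

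The documents give no AE rate, and they disagree on when TMS first occurs, so the number of events affected cannot be estimated. It would be wrong to infer a substantial safety gap or any effect on the trial's results. Recording of SAEs and unexpected events, the seizure rules, and all outcomes and analyses stand as they are.

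**What to change.** Replace the sentence with one cut-off per participant, no later than the first TMS exposure and counting motor-threshold pulses as exposure. For example: *Only conditions present before the first study procedure at Session 1 are baseline. Any condition that starts or worsens after that point is recorded as an AE, at whichever session it is noted.*

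Session 1 is one workable choice. It fits Appendix A, where eligibility is settled by that visit, and it does not depend on which section is right about when thresholding takes place. It also keeps reactions to non-TMS procedures out of baseline, such as those at Session 2, where "The EEG net will be applied". A later cut-off would also serve, provided that it precedes the first pulse.

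In the same amendment, reconcile Sections 2.2, 4, 5.1, 5.2 and 6.2 and Appendix A on which sessions involve TMS.

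The change takes a short replacement text and an alignment of session wording. The downside is somewhat more AE recording, including conditions unrelated to TMS and, with a Session 1 cut-off, some that arise before any TMS. The documents give no basis for estimating how many.
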